10.0 STUDY MANAGEMENT

10.1 Institutional Review Board (IRB) Approval and Consent

It is expected that the IRB will have the proper representation and function in accordance with federally mandated regulations. The IRB should approve the consent form and protocol.

In obtaining and documenting informed consent, the investigator should comply with the applicable regulatory requirement(s), and should adhere to Good Clinical Practice (GCP) and to ethical principles that have their origin in the Declaration of Helsinki.

Before recruitment and enrollment onto this study, the patient will be given a full explanation of the study and will be given the opportunity to review the consent form. Each consent form must include all the relevant elements currently required by the FDA Regulations and local or state regulations. Once this essential information has been provided to the patient and the investigator is assured that the patient understands the implications of participating in the study, the patient will be asked to give consent to participate in the study by signing an IRB-approved consent form.

Prior to a patient's participation in the trial, the written informed consent form should be signed and personally dated by the patient and by the person who conducted the informed consent discussion.

10.2 Required Documentation

Before the study can be initiated at any site, the following documentation must be provided to the Clinical Protocol Office (CPO) at the University of North Carolina.

- A copy of the official IRB approval letter for the protocol and informed consent
- IRB membership list
- CVs and medical licensure for the principal investigator and any sub-investigators who will be involved in the study.
- Form FDA 1572 appropriately filled out and signed with appropriate documentation
- Financial Disclosures
- CAP and CLIA Laboratory certification numbers and institution lab normal values
- Executed clinical research contract

10.3 Registration Procedures

Within 24 hours of subject consent, all subjects are registered in OnCore and all informed consent documentation uploaded into the OnCore Subject Console by a designee from the participating institution. Upon subject registration completion, the designee must email [contact] or call [contact] (M-F 8:30AM – 5:00PM EST) to alert the UNC LCCC Multicenter Office for initial review and assignment. Complete eligibility packets (institutionally-signed eligibility checklist and full source documentation confirming eligibility) are uploaded by the institutional designee into the OnCore Subject Console and the LCCC Multicenter Office concurrently alerted by email or phone ([contact]; [contact]) to begin review. All subjects must have final eligibility verified by the UNC Multicenter Project Manager on behalf of the UNC PI prior to starting treatment. Please allow 24 hours for source to be reviewed and notification of subject eligibility released. All subjects must maintain eligibility from the time of this notification through the beginning of treatment.

10.4 Data Management and Monitoring/Auditing

The CPO Multicenter Office of the UNC LCCC will serve as the coordinating center for this trial. Data will be collected through a web based clinical research platform, OnCore®. Other study institutions will be given a password to directly enter their own data onto the web site via electronic case report forms (eCRFs). Multicenter personnel will coordinate and manage data for quality control assurance and integrity.

All data will be collected and entered into OnCore® by the multicenter study teams at participating institutions. The investigators at each site will allow monitors to review all source documents supporting data entered into OnCore®. The Multicenter Data Coordinator can be reached at [contact] or [name].

All data will be monitored and source data will be verified on selected subjects. Queries will be issued on an ongoing basis on all subjects. Participating sites should respond to data queries within 14 days of receipt. The LCCC

Compliance Committee or their designee will audit trial sites every twelve months while still enrolling or subjects are still on treatment. Participating sites must send source and regulatory documents to LCCC upon request, for remote monitoring and/or audit review.

10.5 Adherence to the Protocol

Except for an emergency situation in which proper care for the protection, safety, and well-being of the study patient requires alternative treatment, the study shall be conducted exactly as described in the approved protocol.

10.5.1 Emergency Modifications

UNC and multicenter site investigators may implement a deviation from, or a change of, the protocol to eliminate an immediate hazard(s) to trial subjects without prior UNC or their respective institution's IRB/IEC approval/favorable opinion.

For Institutions Relying on UNC's IRB:

For any such emergency modification implemented, a UNC IRB modification form must be completed by UNC Research Personnel within five (5) business days of making the change.

For Institutions Relying on Their Own IRB:

For multicenter site investigators relying on their own institution's IRB, as soon as possible after the modification has been made, the implemented deviation or change and the reasons for it should be submitted to:

- The UNC Principal Investigator for agreement
- The multicenter institution's IRB for review and approval. (Once IRB's response is received, this should be forwarded to the Multicenter Regulatory Associate).

10.5.2 Single Patient/Subject Exceptions

Eligibility single subject exceptions are not permitted for Lineberger Comprehensive Cancer Center Investigator Initiated Trials under any circumstances. Other types of single subject exceptions may be allowed if proper regulatory review has been completed in accordance with Lineberger Comprehensive Cancer Center's Single Subject Exceptions Policy.

10.5.3 Other Protocol Deviations/Violations

According to UNC's IRB, a protocol deviation is any unplanned variance from an IRB approved protocol that:

- Is generally noted or recognized after it occurs
- Has no substantive effect on the risks to research participants

- Has no substantive effect on the scientific integrity of the research plan or the value of the data collected
- Did not result from willful or knowing misconduct on the part of the investigator(s).

An unplanned protocol variance is considered a violation if the variance meets any of the following criteria:

- Has harmed or increased the risk of harm to one or more research participants.
- Has damaged the scientific integrity of the data collected for the study.
- Results from willful or knowing misconduct on the part of the investigator(s).
- Demonstrates serious or continuing noncompliance with federal regulations, State laws, or University policies.

If a deviation or violation occurs please follow the guidelines below:

For Institutions Relying on UNC's IRB:

Protocol Deviations: UNC or multicenter site personnel will record the deviation in OnCore®, and report to any sponsor or data and safety monitoring committee in accordance with their policies.

Protocol Violations: Violations should be reported by UNC personnel within one (1) week of the investigator becoming aware of the event using the same IRB online mechanism used to report Unanticipated Problems.

For Institutions Relying on Their Own IRB:

In addition to adhering to the policies regarding protocol compliance set forth by your institution's IRB, the following is also required:

Protocol Deviations: In the event a deviation from protocol procedures is identified, record the deviation in OnCore®.

Protocol Violations: Any protocol violation that occurs must be reported to your IRB per institutional policies and reported to the Multicenter Project Manager within 5 days. UNC-CH will determine if the violation affects the safety of the patient and integrity of the data. Once your institution's IRB response is received, please forward to the Multicenter Regulatory Associate.

Unanticipated Problems:
UNC

Any events that meet the criteria for “Unanticipated Problems” as defined by UNC’s IRB must be reported by the study personnel using the IRB’s web-based reporting system.

Multicenter Sites:

Any events that meet the criteria for “Unanticipated Problems (UPs)” as defined by UNC’s IRB must also be reported to the Multicenter Project Manager. The Multicenter Regulatory Associate will submit reportable events to the UNC IRB using the IRB’s web-based reporting system. Examples of such UPs include a lost or stolen laptop computer that contains sensitive study information.

10.6 Amendments to the Protocol

Should amendments to the protocol be required, the amendments will be originated and documented by the Principal Investigator at UNC. It should also be noted that when an amendment to the protocol substantially alters the study design or the potential risk to the patient, a revised consent form might be required.

For Institutions Relying on UNC’s IRB:

The written amendment, and if required the amended consent form, must be sent to UNC’s IRB for approval prior to implementation.

For Institutions Relying on Their Own IRB:

Investigators must submit the amendment to their institution’s IRB for approval. For multi-center studies, any multicenter site must submit their informed consent revisions to the Multicenter Regulatory Associate prior to submission to their IRB.

10.7 Record Retention

Study documentation includes all eCRFs, data correction forms or queries, source documents, Sponsor correspondence to Investigators, monitoring logs/letters, and regulatory documents (e.g., protocol and amendments, IRB correspondence and approval, signed patient consent forms).

Source documents include all recordings of observations or notations of clinical activities and all reports and records necessary for the evaluation and reconstruction of the clinical research study.

Government agency regulations and directives require that all study documentation pertaining to the conduct of a clinical trial must be retained by the study investigator. In the case of a study with a drug seeking regulatory approval and marketing, these documents shall be retained for at least two years after the last approval of marketing application in an International Conference on Harmonization (ICH) region. In all other cases, study documents should be kept on file until three years after the completion and final study report of this investigational study.

10.8 Obligations of Investigators

The Principal Investigator is responsible for the conduct of the clinical trial at the site in accordance with Title 21 of the Code of Federal Regulations and/or the Declaration of Helsinki. The Principal Investigator is responsible for personally overseeing the treatment of all study patients. The Principal Investigator must assure that all study site personnel, including sub-investigators and other study staff members, adhere to the study protocol and all FDA/GCP/NCI regulations and guidelines regarding clinical trials both during and after study completion.

The Principal Investigator at each institution or site will be responsible for assuring that all the required data will be collected and entered into the eCRFs. Periodically, monitoring visits will be conducted and the Principal Investigator will provide access to his/her original records to permit verification of proper entry of data. At the completion of the study, all eCRFs will be reviewed by the Principal Investigator and will require his/her final signature to verify the accuracy of the data.

12.0 APPENDICES

12.1 Dose Modification & Toxicity Management Guidelines for Durvalumab

Toxicity grades per NCI-CTCAE criteria version 5.0.

12.1.1 Immune-Mediated Reactions - General

See next page for details. Note that recommended dose holds may result in lack of planned synchrony between radiation and systemic therapy. In the case that a patient requires a hold of dose due to toxicity, which recovers to grade 1 or less and the patient is eligible to restart therapy, this will be allowed. **The lack of synchrony will not be considered a deviation. Imaging timing will be potentially delayed due to such a situation and this will also not be a deviation.**

Dosing Modification and Toxicity Management Guidelines for Immune-Mediated, Infusion-Related, and Non-Immune-Mediated Reactions (MEDI4736 Monotherapy or Combination Therapy with Tremelimumab or Tremelimumab Monotherapy) 17 October 2019 Version (CTCAE v5.0)

General Considerations regarding Immune-Mediated Reactions

Dose Modifications		Toxicity Management
Drug administration modifications of study drug/study regimen will be made to manage potential immune-related AEs based on severity of treatment-emergent toxicities graded per NCI CTCAE v5.0.		
It is recommended that management of immune-mediated adverse events (imAEs) follows the guidelines presented in this table:
 
– It is possible that events with an inflammatory or immune mediated mechanism could occur in nearly all organs, some of them not noted specifically in these guidelines.– Whether specific immune-mediated events (and/or laboratory indicators of such events) are noted in these guidelines or not, patients should be thoroughly evaluated to rule out any alternative etiology (e.g., disease progression, concomitant medications, and infections) to a possible immune-mediated event. In the absence of a clear alternative etiology, all such events should be managed as if they were immune related. General recommendations follow.– Symptomatic and topical therapy should be considered for low-grade (Grade 1 or 2, unless otherwise specified) events.– For persistent (>3 to 5 days) low-grade (Grade 2) or severe (Grade ≥ 3) events, promptly start prednisone 1 to 2 mg/kg/day PO or IV equivalent.– Some events with high likelihood for morbidity and/or mortality – e.g., myocarditis, or other similar events even if they are not currently noted in the guidelines – should progress rapidly to high dose IV corticosteroids (methylprednisolone at 2 to 4 mg/kg/day) even if the event is Grade 2, and if clinical suspicion is high and/or there has been clinical confirmation. Consider, as necessary, discussing with the study physician, and promptly pursue specialist consultation.– If symptoms recur or worsen during corticosteroid tapering (28 days of taper), increase the corticosteroid dose (prednisone dose [e.g., up to 2 to 4 mg/kg/day PO or IV equivalent]) until stabilization or improvement of symptoms, then resume corticosteroid tapering at a slower rate (>28 days of taper).– More potent immunosuppressives such as TNF inhibitors (e.g., infliximab; also refer to the individual sections of the imAEs for specific type of immunosuppressive) should be considered for events not responding to

In addition to the criteria for permanent discontinuation of study drug/study regimen based on CTC grade/severity (table below), permanently discontinue study drug/study regimen for the following conditions:
 
• Inability to reduce corticosteroid to a dose of ≤ 10 mg of prednisone per day (or equivalent) within 12 weeks of the start of the immune-mediated adverse event (imAE)• Grade 3 recurrence of a previously experienced treatment-related imAE following resumption of dosing	
Grade 1 No dose modification
 
Grade 2 Hold study drug/study regimen dose until Grade 2 resolution to Grade ≤ 1. If toxicity worsens, then treat as Grade 3 or Grade 4.
 
Study drug/study regimen can be resumed once event stabilizes to Grade ≤ 1 after completion of steroid taper.
 
Patients with endocrinopathies who may require prolonged or continued steroid replacement can be retreated with study drug/study regimen on the following conditions:
 
1. The event stabilizes and is controlled.2. The patient is clinically stable as per Investigator or treating physician's clinical judgement.3. Doses of prednisone are at ≤ 10 mg/day or equivalent.	

Grade 3 Depending on the individual toxicity, study drug/study regimen may be permanently discontinued. Please refer to guidelines below.
		

Dosing Modification and Toxicity Management Guidelines for Immune-Mediated, Infusion-Related, and Non-Immune-Mediated Reactions (MEDI4736 Monotherapy or Combination Therapy with Tremelimumab or Tremelimumab Monotherapy) 17 October 2019 Version (CTCAE v5.0)

General Considerations regarding Immune-Mediated Reactions

Dose Modifications		Toxicity Management
Grade 4	Permanently discontinue study drug/study regimen. Note: For asymptomatic amylase or lipase levels of >2X ULN, hold study drug/study regimen, and if complete work up shows no evidence of pancreatitis, study drug/study regimen may be continued or resumed. Note: Study drug/study regimen should be permanently discontinued in Grade 3 events with high likelihood for morbidity and/or mortality – e.g., myocarditis, or other similar events even if they are not currently noted in the guidelines. Similarly, consider whether study drug/study regimen should be permanently discontinued in Grade 2 events with high likelihood for morbidity and/or mortality – e.g., myocarditis, or other similar events even if they are not currently noted in the guidelines – when they do not rapidly improve to Grade <1 upon treatment with systemic steroids and following full taper Note: There are some exceptions to permanent discontinuation of study drug for Grade 4 events (i.e., hyperthyroidism, hypothyroidism, Type 1 diabetes mellitus).	systemic steroids. Progression to use of more potent immunosuppressives should proceed more rapidly in events with high likelihood for morbidity and/or mortality – e.g., myocarditis, or other similar events even if they are not currently noted in the guidelines – when these events are not responding to systemic steroids. 
With long-term steroid and other immunosuppressive use, consider need for Pneumocystis jirovecii pneumonia (PJP, formerly known as Pneumocystis carinii pneumonia) prophylaxis, gastrointestinal protection, and glucose monitoring.Discontinuation of study drug/study regimen is not mandated for Grade 3/Grade 4 inflammatory reactions attributed to local tumor response (e.g., inflammatory reaction at sites of metastatic disease and lymph nodes). Continuation of study drug/study regimen in this situation should be based upon a benefit-risk analysis for that patient.

AE Adverse event; CTC Common Toxicity Criteria; CTCAE Common Terminology Criteria for Adverse Events; imAE immune-mediated adverse event; IV intravenous; NCI National Cancer Institute; PO By mouth.

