Grade 3 or 4	For Grade 3: Hold study drug/study regimen until resolution to Grade ≤ 1 or baseline. If temporarily holding the study drug/study regimen does not provide improvement of the Grade 3 skin rash to Grade ≤ 1 or baseline within 30 days, then permanently discontinue study drug/study regimen. For Grade 4 (or life-threatening): Permanently discontinue study drug/study regimen.		For Grade 3 or 4 (or life-threatening): 
– Consult Dermatology.– Promptly initiate empiric IV methylprednisolone 1 to 4 mg/kg/day or equivalent.– Consider hospitalization.– Monitor extent of rash [Rule of Nines].– Consider skin biopsy (preferably more than 1) as clinically feasible.– Once the patient is improving, gradually taper steroids over ≥ 28 days and consider prophylactic antibiotics, antifungals, and anti-PJP treatment (refer to current NCCN guidelines for treatment of cancer-related infections).^a– Consider, as necessary, discussing with study physician.
Endocrinopathy (e.g., hyperthyroidism, thyroiditis, hypothyroidism, Type 1 diabetes mellitus, hypophysitis, hypopituitarism, and adrenal insufficiency; exocrine event of amylase/lipase increased)	Any Grade (depending on the type of endocrinopathy, refer to NCI CTCAE v5.0 for defining the CTC grade/severity)	General Guidance	For Any Grade: 
– Consider consulting an endocrinologist for endocrine events.– Consider, as necessary, discussing with study physician.– Monitor patients for signs and symptoms of endocrinopathies. Non-specific symptoms include headache, fatigue, behavior changes, changed mental status, vertigo, abdominal pain, unusual bowel habits, polydipsia, polyuria, hypotension, and weakness.– Patients should be thoroughly evaluated to rule out any alternative etiology (e.g., disease progression including brain metastases, or infections).– Depending on the suspected endocrinopathy, monitor and evaluate thyroid function tests: TSH, free T3 and free T4 and

also included in this
section)

other relevant endocrine and related labs (e.g., blood glucose and ketone levels, HgA1c).

- For asymptomatic elevations in serum amylase and lipase $>\text{ULN}$ and $<3 \times \text{ULN}$, corticosteroid treatment is not indicated as long as there are no other signs or symptoms of pancreatic inflammation.

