Grade 3 or 4	
For Grade 3 or 4 endocrinopathy other than hypothyroidism and Type 1 diabetes mellitus, hold study drug/study regimen dose until endocrinopathy symptom(s) are controlled.
 
Study drug/study regimen can be resumed once event stabilizes and after completion of steroid taper.
 
Patients with endocrinopathies who may require prolonged or continued steroid replacement (e.g., adrenal insufficiency) can be retreated with study drug/study regimen on the following conditions:
 
1. The event stabilizes and is controlled.2. The patient is clinically stable as per investigator or treating physician's clinical judgement.	
For Grade 3 or 4:
 
– Consult endocrinologist to guide evaluation of endocrine function and, as indicated by suspected endocrinopathy and as clinically indicated, consider pituitary scan. Hospitalization recommended.– For all patients with abnormal endocrine work up, except those with isolated hypothyroidism or Type 1 DM, and as guided by an endocrinologist, promptly initiate empiric IV methylprednisolone 1 to 2 mg/kg/day or equivalent, as well as relevant hormone replacement (e.g., hydrocortisone, sex hormones).– For adrenal crisis, severe dehydration, hypotension, or shock, immediately initiate IV corticosteroids with mineralocorticoid activity.– Isolated hypothyroidism may be treated with replacement therapy, without study drug/study regimen interruption, and without corticosteroids.– Isolated Type 1 diabetes mellitus may be treated with appropriate diabetic therapy, without study drug/study regimen interruption, and without corticosteroids.– Once patients on steroids are improving, gradually taper immunosuppressive steroids (as appropriate and with guidance of endocrinologist) over ≥ 28 days and consider prophylactic

		3. Doses of prednisone are ≤ 10 mg/day or equivalent.	antibiotics, antifungals, and anti-PJP treatment (refer to current NCCN guidelines for treatment of cancer-related infections). ^a

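### At Grade 4, Appendix 12.1.1 requires permanent discontinuation for adrenal insufficiency, hypophysitis, hypopituitarism and thyroiditis, Appendix 12.1.2 allows a hold with optional resumption, and no text says which governs

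*Combined protocol and SAP*

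**What the plan says.** Section 5.3 refers sites to Appendix 12.1 for dose modification and lists 12.1.1 (general) and 12.1.2 (specific reactions) side by side.

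**Appendix 12.1.1, Grade 4 row.** The row opens: "Permanently discontinue study drug/study regimen. Note: For asymptomatic amylase or lipase levels of >2X ULN, hold study drug/study regimen". A later note reads: "There are some exceptions to permanent discontinuation of study drug for Grade 4 events (i.e., hyperthyroidism, hypothyroidism, Type 1 diabetes mellitus".

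**Appendix 12.1.2, Endocrinopathy.** The section names hyperthyroidism and thyroiditis and continues with "hypothyroidism, Type 1 diabetes mellitus, hypophysitis, hypopituitarism, and adrenal insufficiency". It also takes in amylase or lipase increase. Its Grade 3 or 4 row says: "For Grade 3 or 4 endocrinopathy other than hypothyroidism and Type 1 diabetes mellitus, hold study drug/study regimen dose until endocrinopathy symptom(s) are controlled". It then adds: "Study drug/study regimen can be resumed once event stabilizes and after completion of steroid taper". Patients who need prolonged or continued steroid "replacement (e.g., adrenal insufficiency) can be retreated with study drug/study regimen on the following conditions"; the conditions concern control of the event, clinical stability and the prednisone dose.

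**Deference between the tables.** The Grade 3 row of 12.1.1 hands over to the specific table: "Depending on the individual toxicity, study drug/study regimen may be permanently discontinued. Please refer to guidelines below". The Grade 4 row has no such hand-over.

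**The concern.** A Grade 4 adrenal insufficiency falls under both tables. Under 12.1.1 the drug is stopped for good, because the event is not among the named exceptions. Under 12.1.2 the drug is held and may be restarted. The same holds for hypophysitis, hypopituitarism and thyroiditis.

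These events are foreseeable. Section 8.2 lists all four among the events of special interest observed with durvalumab. The trial is multi-center (Section 1.1), and Section 10.5 requires conduct exactly to protocol outside emergencies. Two sites could reach different conclusions about re-dosing after a life-threatening event, each with protocol text in support. A site that re-doses under 12.1.2 could also be recorded as departing from 12.1.1.

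**Working it through.** No arithmetic is involved beyond a count. The check sets the two tables side by side and then looks for a rule that ranks them.

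**Step 1. Compare the instructions, event by event, at Grade 4.**

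| Event named in the 12.1.2 endocrinopathy section | 12.1.1, Grade 4 row | 12.1.2, Grade 3 or 4 row | Compatible? |
|---|---|---|---|
| Adrenal insufficiency | Not excepted: permanent stop | Hold; may resume; given as the example for retreatment on steroid replacement | No |
| Hypophysitis | Not excepted: permanent stop | Hold; may resume | No |
| Hypopituitarism | Not excepted: permanent stop | Hold; may resume | No |
| Thyroiditis | Not excepted: permanent stop | Hold; may resume | No |
| Hyperthyroidism | Excepted | Hold; may resume | Yes |
| Hypothyroidism | Excepted | Outside the hold | Yes |
| Type 1 diabetes mellitus | Excepted | Outside the hold | Yes |

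Of the seven endocrine diagnoses, 7 − 3 = 4 carry a conflict. Amylase or lipase increase is left out of the count, because asymptomatic elevation has its own note in the Grade 4 row of 12.1.1.

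**Step 2. Is Grade 4 really within the 12.1.2 row?** Yes. The row is labelled Grade 3 or 4, its hold instruction names both grades, and its management column deals with adrenal crisis and shock. It contains no separate Grade 4 stop. The other sections of 12.1.2 (pneumonitis, diarrhea/colitis, hepatitis, nephritis, rash, neurotoxicity, neuromotor syndromes, myocarditis and myositis) each carry a permanent stop at Grade 4 or an equivalent laboratory threshold. Endocrinopathy is the only one that does not.

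**Step 3. Does any text rank the tables at Grade 4?**

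- Section 5.3 lists both without an order of precedence.
- The Grade 3 row of 12.1.1 defers to the specific guidelines; the Grade 4 row does not.
- 12.1.1 has wording on retreating endocrinopathy patients who need steroid replacement, but it stands in the Grade 2 row.
- Section 5.8 withdraws patients for unacceptable adverse events, which does not say how these four are to be classed.

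No ranking was found.

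**Step 4. How far apart are the instructions?** One is a mandatory permanent stop. The other is a hold after which resumption is allowed under conditions. A site that never resumes breaches neither table, so the conflict bites only where a site wishes to re-dose.

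**Step 5. Does it reach the endpoints?**

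- Disease-free survival runs from day 1 of treatment to recurrence or death (Section 3.1.1). Stopping drug is neither an event nor a stated censoring rule.
- A regimen-attributed Grade 4 event in the acute window of Section 3.2.1 already makes the patient a case in the Grade 3-5 acute rate of Section 9.3, whichever table the site then follows. Only later individual events or grades could differ.
- The visible endpoints in Section 3 and the analyses in Section 9 include no discontinuation count.

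**The case against.** The strongest reply is structural. 12.1.1 is headed as general considerations and 12.1.2 as specific reactions, so a reader would naturally let the specific row prevail. Two details support this. First, the three-item list does not exhaust the departures from a Grade 4 stop: the same table treats asymptomatic amylase or lipase elevation separately, and does not mandate a stop for inflammatory reactions attributed to local tumor response. Second, hyperthyroidism is on the list yet follows the same hold-and-resume row as adrenal insufficiency, so the note could be a loose pointer to the endocrinopathy section. Section 8.2 adds that the guidelines are there to assist clinical judgment.

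This makes specific-over-general a plausible reading, but the text does not establish it. The extra departures do not cover the four events. The exception note is introduced by i.e., names three endocrine conditions and omits these four. If 12.1.2 simply prevailed, the note would not be needed. The drafters wrote a deferral into the Grade 3 row and none into the Grade 4 row.

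A reader might also infer that the tables give opposite orders. They do not, because 12.1.2 permits resumption and does not require it. Nor does the conflict extend to every endocrinopathy section entry outside the three exceptions, given the separate amylase and lipase note.

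**Conclusion.** The inconsistency is real, is in the current text, and concerns four named events at Grade 4. It should be resolved because it governs whether a patient may be re-dosed after a life-threatening event. It is a safety and uniform-conduct point, and the conclusion rests on the wording alone.

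Its size in patients cannot be given, because the documents state no event rate. A reader might express it as one patient in 18 (1/18 = 5.6%), or as five of six doses at stake if the event follows the first dose (6 − 1 = 5). Neither measures expected impact: the first is true of any single-patient matter in this trial, and the second assumes the earliest possible timing. A reader might also infer that the toxicity result or the disease-free survival estimate depends on which table a site used. The documents do not support that: the patient's status as a Grade 3-5 case in the acute window is the same under both tables, and no effect on disease-free survival is shown.

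**What to change.** Reconcile the Grade 4 row of Appendix 12.1.1 with the endocrinopathy Grade 3 or 4 row of Appendix 12.1.2, so that each named endocrine event, thyroiditis included, has one Grade 4 instruction. State which table governs when the two differ. The clinical team and the drug supplier, whose guideline dated 17 October 2019 is the source of the wording, should decide the content; no rule is proposed here.

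The cost is a short amendment with IRB approval under Section 10.6 and a memo to sites. It needs no extra patients, visits or procedures.
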